## 1.3 Schedule of Events

The screening evaluation will only be performed after the subject has agreed to participate and has signed and dated the ICF. No treatment or trial-related procedures will be initiated before the informed consent is signed. The Day 1 visit must be performed, at the latest, 30 days after the screening visit. For Cohort 2 only (healthy subjects), the sample collections on Day 1 can be performed on the same day as the screening visit or on separate visits as per the schedule of events, at the investigator's discretion.

The screening evaluation will be performed according to the inclusion and exclusion criteria. If the subject fulfills all inclusion criteria and no exclusion criteria, he or she may be included in the trial.

**Table 1** and **Table 2** provide a description of the procedures to be performed at each visit for Cohort 1 and Cohort 2, respectively.

Unless specified otherwise, the trial assessments scheduled during the trial visits must be performed before the IMP application for subjects in Cohort 1. If assessments are scheduled for the same nominal time, then the assessments should occur in the following order:

- Patient-reported outcomes
- Investigator assessments
- Vital signs
- Medical photographs
- Collection of skin samples

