**Table 1: Schedule of Events for Cohort 1 (Subjects with FFA)**

Trial Visits	Screening	Treatment Period							Follow-Up	ET
		Vehicle-Controlled				OLE				
		Day 1	Week 4	Week 8	Week 12	Week 16	Week 20	Week 24	Week 26	-
		V1	V2	V3	V4	V5	V6	V7	V8	V9
Window (days)	-30 to -1	-	±2	±2	±2	±4	±4	±4	±4	-
Informed consent	X									
Demographics	X									
Medical and surgical history	X	X								
Inclusion-exclusion criteria	X	X								
Pregnancy test a	X	X	X	X	X	X	X	X	X	X
Clinical laboratory tests (biochemistry and hematology)	X	X	X	X	X	X	X	X		X
TSH and reflex free T4	X									
Serology (HBV [HBsAg, anti-HBc], HCV, HIV)	X									
Electrocardiogram	X									
Complete Physical examination	X				X			X	X	X
Brief Physical examination		X	X	X		X	X			
Vital signs b	X	X	X	X	X	X	X	X	X	X
Identification of a lesional target area on the scalp and of a non lesional area (eg. occipital scalp) c	X	X								

Trial Visits	Screening	Treatment Period							Follow-Up	ET		
		Vehicle-Controlled				OLE						
		Day 1	Week 4	Week 8	Week 12	Week 16	Week 20	Week 24				
	V1	V2	V3	V4	V5	V6	V7	V8	V9	-		
Window (days)	-30 to -1	-	±2	±2	±2	±4	±4	±4	±4	-		
Perifollicular erythema and scale evaluation of the lesional target area	X	X	X	X	X	X	X	X		X		
Pruritus NRS d	X	X	X	X	X	X	X	X		X		
Burning Sensation NRS d	X	X	X	X	X	X	X	X		X		
Pain NRS d	X	X	X	X	X	X	X	X		X		
LPPAI		X	X	X	X	X	X	X		X		
FFASS		X	X	X	X	X	X	X		X		
Hair counts/Trichoscopy		X			X			X		X		
Hair line measurements e		X			X			X		X		
Medical photographs f		X			X			X		X		
Randomization		X										
IMP application at site		X	X	X	X	X	X					
IMP application BID g		X-----X										
IMP distribution		X	X	X	X	X	X					
IMP collection and/or accountability and/or compliance			X	X	X	X	X	X		X		
Subject diary distribution/collection/review	X	X	X	X	X	X	X	X		X		
Local tolerability assessments h		X	X	X	X	X	X	X		X		

Trial Visits	Screening	Treatment Period							Follow-Up	ET		
		Vehicle-Controlled				OLE						
		Day 1	Week 4	Week 8	Week 12	Week 16	Week 20	Week 24				
	V1	V2	V3	V4	V5	V6	V7	V8	V9	-		
Window (days)	-30 to -1	-	±2	±2	±2	±4	±4	±4	±4	-		
Skin biopsies collection i,j		X			X							
Adhesive skin tape strip samples k		X			X							
Skin microbiome samples l		X			X							
Concomitant medication	X	X	X	X	X	X	X	X	X	X		
Adverse events collection	X	X	X	X	X	X	X	X	X	X		

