Abbreviations: anti-HBc, antibody to hepatitis B core antigen; BID, twice daily; ET, early termination; FFA, frontal fibrosing alopecia; FFASS, Frontal Fibrosing Alopecia Severity Score; HBV, hepatitis B virus; HBsAg, hepatitis B surface antigen; HCV, hepatitis C virus; HIV, human immunodeficiency virus; IMP, investigational medicinal product; LPPAI, lichen planopilaris activity index; NRS, Numerical Rating Scale; OLE, open-label extension; TSH, thyroid-stimulating hormone; V, visit.

a For female subjects of childbearing potential, serum pregnancy test at screening and urine pregnancy test at other specified visits.

b Including height and weight. Height will be measured only at screening.

c The lesional target area should be treated with the IMP and should be approximately 3 cm x 6 cm (or equivalent). However, a smaller lesional target area can be selected if tape stripping is performed from the same area where trichoscopy/hair counts is performed or if sample is collected adjacent/close to the lesional target area (refer to Section 8.3.2 for details). If needed, two small lesional target areas (totalling approximately the same size) could be selected to allow for skin samples collection.

d Subjects will complete their NRS at home on a daily basis starting approximately 7 days prior to Day 1 and up to Day 8. On Day 1, the NRS will be completed at the site prior to the first IMP application. After Day 8, the NRS will be completed at the site at the specified visits only.

e Hair line measurements of lateral canthus (right and left) to hairline, lower glabellar crease to hair line, top of frontalis muscle to hair line, and mid brow to hair line (right and left).

f Medical photographs of the target area and the entire scalp (including the frontal hair line and right and left hair line areas).

g The morning application will be on site on visit days. Other IMP applications will be done at home. The first application of the OLE (delgocitinib cream 20 mg/g) is on the morning of Week 12, after all efficacy assessments and skin sample collections are completed. The last application of the OLE is the evening prior to the Week 24 visit. No IMP application will be done on the day of the Week 24 visit.

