### 3 OBJECTIVES AND ENDPOINTS

OBJECTIVES	ENDPOINTS
Primary	
To assess molecular signature changes following topical application of delgocitinib cream 20 mg/g in subjects with FFA	Primary endpoint: 

Change in expression of CXCL9, CXCL10, and IFN-<math>\gamma</math> from baseline to Week 12.

Secondary	Safety endpoint during the vehicle-controlled treatment period: 

Number of TEAEs from baseline to Week 12.

Exploratory	Exploratory safety endpoint: 

Number of TEAEs during the OLE (up to Week 26)

 Exploratory efficacy endpoints during the vehicle-controlled treatment period: 

Change in LPPAI score from baseline to Weeks 4, 8, and 12.

Change in FFASS score from baseline to Weeks 4, 8, and 12.

Change in target area perifollicular erythema score from baseline to Weeks 4, 8, and 12.

Change in target area perifollicular scale score from baseline to Weeks 4, 8, and 12.

Change in pruritus NRS score from baseline to Days 2, 3, 4, 5, 6, 7, 8, and Weeks 4, 8, and 12.

Change in burning sensation NRS score from baseline to Days 2, 3, 4, 5, 6, 7, 8, and Weeks 4, 8, and 12.

Change in pain NRS score from baseline to Days 2, 3, 4, 5, 6, 7, 8, and Weeks 4, 8, and 12.

Proportion of subjects with a 3-point reduction* in pruritus NRS score from baseline to Days 2, 3, 4, 5, 6, 7, 8, and Weeks 4, 8, and 12.

Proportion of subjects with a 4-point reduction* in pruritus NRS score from baseline to Days 2, 3, 4, 5, 6, 7, 8, and Weeks 4, 8, and 12.

OBJECTIVES	ENDPOINTS
	

• Proportion of subjects with a 3-point reduction* in burning sensation NRS score from baseline to Days 2, 3, 4, 5, 6, 7, 8, and Weeks 4, 8, and 12.

• Proportion of subjects with a 4-point reduction* in burning sensation NRS score from baseline to Days 2, 3, 4, 5, 6, 7, 8, and Weeks 4, 8, and 12.

• Proportion of subjects with a 3-point reduction* in pain NRS score from baseline to Days 2, 3, 4, 5, 6, 7, 8, and Weeks 4, 8, and 12.

• Proportion of subjects with a 4-point reduction* in pain NRS score from baseline to Days 2, 3, 4, 5, 6, 7, 8, and Weeks 4, 8, and 12.

• Change in target area hair counts/trichoscopy via fotofinder trichovision from baseline to Week 12.

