### 9.3.4 Safety Analyses

#### 9.3.4.1 Vehicle-Controlled Treatment Period

##### Cohort 1:

All safety data, including AEs and SAEs will be presented and tabulated according to the Medical Dictionary for Regulatory Activities (MedDRA) classification. Descriptions of AEs will include the start date, the stop date (if it resolved), the severity and seriousness of the AE, the causality of the AE to IMP, and the outcome. The focus in this protocol will be the number of treatment-emergent adverse events (TEAEs).

Adverse events will be considered in vehicle-controlled treatment period or OLE depending on the onset date – if the AE onset date was before Week 12, the AE will be considered as a vehicle-controlled treatment period AE. If the AE had an onset on or after Week 12, the AE will be considered as an OLE AE.

Reported AEs will be summarized by the number of subjects reporting the events, as well as by System Organ Class (SOC), PT, severity, seriousness, and relationship to IMP. For the summary of AEs by severity, each subject will be counted only once within a SOC or a PT by using the AEs with the highest intensity within each category for each analysis. For the summary of AEs by relationship to IMP, each subject will be counted only once within a SOC or a PT by using the AEs with the greatest reported relationship within each category. For the summary of AEs by relationship to IMP and severity, each subject will be counted only once within a SOC or a PT by using (1) the greatest reported relationship followed by (2) the highest reported intensity.

All information pertaining to AEs noted during the trial will be listed by subject, detailing verbatim, SOC, PT, start date, stop date, intensity, outcome, and relationship to IMP. The AE onset will also be shown relative (in number of days) to the day of IMP administration. Serious adverse events will be tabulated by treatment group, relationship to the IMP, and a reference to the occurrence of the SAEs to the relative day of dosing.

AESIs will be listed. No narratives for AESIs will be written in the study report.

Results from laboratory analyses and vital signs will be tabulated by treatment and visit using descriptive statistics. The value at each visit as well as the change from baseline will be presented descriptively.

Clinically significant changes in laboratory analyses and vital signs, and new findings on local tolerability assessments and physical examination will be recorded as AEs.

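### AEs that arise at the Week 12 visit before the first open-label dose are counted as OLE events and leave the secondary endpoint

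*Combined protocol and SAP*

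**What the plan says.** The period rule is in Section 9.3.4.1 (Cohort 1). On one side, "if the AE onset date was before Week 12, the AE will be considered as a vehicle-controlled treatment period AE". On the other, "If the AE had an onset on or after Week 12, the AE will be considered as an OLE AE". Neither half refers to a dose.

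The secondary endpoint in Section 3 is "Number of TEAEs from baseline to Week 12". TEAEs during the OLE are the exploratory safety endpoint.

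Section 1.3 fixes the order of events within a visit: "Unless specified otherwise, the trial assessments scheduled during the trial visits must be performed before the IMP application for subjects in Cohort 1". Footnote g of Table 1 adds that the first OLE application "is on the morning of Week 12, after all efficacy assessments and skin sample collections are completed". Table 1 schedules biochemistry and hematology, vital signs, a complete physical examination and a biopsy at Week 12.

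Findings from these procedures can become AEs. Section 9.3.4.1 states: "Clinically significant changes in laboratory analyses and vital signs, and new findings on local tolerability assessments and physical examination will be recorded as AEs".

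**The concern.** The rule uses a visit label to divide two treatments that change over in the middle of that visit. Everything found before the morning application at Week 12 was found after randomised treatment only, yet it is booked to the open-label period.

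The visit matters for controlled safety. It is one of three scheduled post-baseline laboratory visits in the vehicle-controlled period (Weeks 4, 8 and 12), and it holds that period's only complete physical examination after screening. A silent abnormality first detected there and dated to the sample is missing from the vehicle-controlled count. In a vehicle-randomised subject it also appears in the summary by OLE treatment (Section 9.3.4.2), under a drug not yet applied.

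**Working it through.** The plan states no figure on this point, so there is none to reproduce. The check sets the rule against the order of events at the visit.

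**Step 1: what comes before the first OLE application, and where the rule puts it.** The table takes Week 12 as the visit and assumes the AE is dated to that day.

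| Source of AE at Week 12 | Timing against first OLE application | Treatment applied so far | Period under 9.3.4.1 |
|---|---|---|---|
| Laboratory tests, vital signs, physical examination | Before (1.3) | Randomised only | OLE |
| Biopsy complication starting before the application | Before (Table 1, footnote g) | Randomised only | OLE |
| Biopsy complication starting after the application | After | Open-label delgocitinib | OLE |
| Local tolerability | About 30 minutes after (8.2.6) | Open-label delgocitinib | OLE |
| Symptom elicited at the visit with an earlier start date | Before | Randomised only | Vehicle-controlled |

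The first two rows are misplaced. The other three are right.

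**Step 2: comparison with the plan's other OLE definitions.** Section 9.3.2 ties the OLE safety baseline to the last assessment before the first delgocitinib dose, and Section 9.3.4.2 uses it for subjects who had vehicle. Normally that is the pre-dose Week 12 value. For such a subject, one abnormal sample is both the pre-delgocitinib baseline and, as an AE, an event of the open-label delgocitinib period.

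**Step 3: subjects never dosed in the OLE.** The OLE safety analysis set (Section 9.2) requires at least one OLE dose. A subject with a Week 12 AE who takes none has an AE labelled OLE but is outside that set. The AE is not a vehicle-controlled AE either, so it can drop out of both summaries.

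**Step 4: can the collected data repair this?** AE onset is collected as a date (Sections 8.5.5 and 8.5.6). Clinic doses carry date and time (Section 6.3.2). The flag in Section 8.5.6 for onset before treatment refers to the first IMP administration, not to the first OLE application. The listing gives days only: "The AE onset will also be shown relative (in number of days) to the day of IMP administration". Same-day events therefore cannot be sorted reliably into before and after the dose.

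**Step 5: scale.** The documents give no rate. As an assumption, let a proportion p of subjects have a pre-dose AE dated to the Week 12 visit. The expected number leaving the secondary endpoint is 30 × p, and the number in the vehicle arm is 15 × p.

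| Assumed p | 30 × p | 15 × p |
|---|---|---|
| 1% | 0.3 | 0.15 |
| 2% | 0.6 | 0.3 |
| 5% | 1.5 | 0.75 |
| 10% | 3.0 | 1.5 |

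These figures show scale only. They are not estimates.

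**The case against.** The strongest reply is that Table 1 and footnote g use Week 12 as a visit, and the first OLE application falls on that same day. With onset recorded by date, rewording the cut as the date of that application would move no event. This stands: the practical defect is a missing before/after-dose flag.

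It can also be said that the rule follows the plan's own convention. Section 9.3.2 treats AEs starting on the date of first treatment as post-baseline, so same-day events go to the period that opens that day. That is a fair account of a tie-break. On Day 1, however, Section 8.5.6 records whether the AE preceded the first dose, and the event stays within the randomised period. At Week 12 there is no such record, and the event leaves that period.

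Other mitigation is real. OLE summaries are also given by randomised group, every AE is listed with its relationship to IMP, and no inferential safety statistics are planned. Abnormal laboratory results are to be reported as the underlying diagnosis where possible (Section 8.5.5), so onset need not be the visit date. Section 9.3.1 leaves safety definitions to a separate SAP that is not among the documents reviewed. That SAP could correct the rule, but it could equally copy the one already written.

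A reader might infer three stronger points that the documents do not support:

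- **A biased comparison between arms.** The rule is identical in both arms, and nothing shows a direction.
- **Whole days misplaced through the ±2-day visit window.** This needs Week 12 to mean a nominal study day. No passage says so, and the schedule uses it as a visit.
- **All Week 12 biopsy complications misplaced.** Those starting after the application belong to the OLE under either cut.

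**Conclusion.** The point holds as a same-day misclassification. The written rule removes from the secondary endpoint AEs that arose under randomised treatment only. In vehicle-randomised subjects it places them under open-label delgocitinib before any was applied. It can also leave an AE of a subject never dosed in the OLE in neither period summary.

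The size is small: events dated to one visit day, in descriptive counts, in about 30 subjects. The true number cannot be computed from the documents. The conclusion rests on Week 12 meaning the visit, on the procedures being done in the stated order, and on the AE being dated to the visit day. It is still worth correcting, because the rule governs the only secondary endpoint and the plan's other OLE safety definitions are already tied to a dose.

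**What to change.** Make the correction in the separate SAP, with one addition to the eCRF:

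- Define the period cut as the first OLE application, and state that Week 12 means the actual visit and not a nominal day.
- Add an AE flag for onset before the first OLE application, modelled on the one in Section 8.5.6. Without it, the new definition cannot separate same-day events.
- Keep flagged AEs in the vehicle-controlled summary and in the secondary endpoint.
- Keep all AEs of subjects never dosed in the OLE in the vehicle-controlled summary.
- Leave AEs that start after the application in the OLE, including Week 12 local tolerability findings and delayed biopsy complications. Moving the whole visit day to the vehicle-controlled period would misplace these.

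The cost is one eCRF field, a few lines of SAP text and minor programming. No visit or procedure changes.

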## 2.2 Risk/Benefit Assessment

### 2.2.1 Known Potential Risks

A total of 15 clinical trials, 1 with oral delgocitinib (sponsored by JT), 11 with delgocitinib ointment (7 sponsored by JT and 4 sponsored by LEO Pharma A/S), and 3 with delgocitinib cream (sponsored by LEO Pharma A/S), have been completed and 2 clinical trials with delgocitinib cream are currently ongoing (sponsored by LEO Pharma A/S). In total, 54 subjects were dosed orally with delgocitinib (at doses between 1 and 100 mg) and 1635 subjects were exposed topically to delgocitinib ointment (1165 subjects at concentrations between 0.3 and 30 mg/g) or delgocitinib cream (470 subjects at concentrations between 1 and 20 mg/g).

Delgocitinib ointment and delgocitinib cream were well tolerated in the conducted clinical trials and systemic exposure to delgocitinib has been low. No clinical indication of any phototoxic potential was observed for delgocitinib cream when single occlusive application of delgocitinib was followed by light exposure in healthy subjects. Potential risks to humans that could arise from use of delgocitinib cream are local skin infection, and acneiform eruptions, which have been reported in clinical trials with delgocitinib ointment. Only few serious adverse events (SAEs) were reported in the completed clinical trials. Except for one, all SAEs were considered not related to treatment. There was no pattern in the reported preferred terms (PT). The one related SAE was an event of *Kaposi's varicelliform eruption* reported in a JT trial with delgocitinib ointment in Japanese subjects. The subject experiencing this event was hospitalized, and the event was resolved.

Generally, no clinically significant changes in laboratory test values, in systolic blood pressure, diastolic blood pressure, pulse rate, or body temperature were observed in subjects exposed to delgocitinib cream. Lymphocytopenia was observed in oral nonclinical toxicity studies and is considered a potential clinical consequence of systemic levels of delgocitinib. Lymphocytopenia is therefore considered an important potential risk for delgocitinib cream.

Further information related to nonclinical and clinical studies is available in the Investigator Brochure (IB).

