## **6.2 Preparation/Handling/Storage/Accountability**

### **6.2.1 Preparation/Storage/Handling**

All IMPs must be stored in a secure environmentally controlled and monitored area in accordance with the labelled storage conditions with access limited to the investigator and authorized site staff. The IMPs may only be supplied by authorized site staff and may only be given to subjects enrolled into the Cohort 1 of the trial.

Investigational medicinal products will be dispensed by the site to the subject in Cohort 1 at the visits specified in [Table 1](#). Subjects are to return all IMPs (used and unused) to the site. The tubes will be weighed prior to dispensing and upon return, and the weight will be recorded in the source documents and electronic case report form (eCRF). Each subject will be instructed on the importance of returning IMP at the next trial visit and on taking the product as prescribed. If a subject does not return IMP, he or she will be instructed to return it as soon as possible.

More details on the application methods are described in the study manual.

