**Table 7: Clinical Laboratory Testing (Cohort 1)**

Laboratory Testing	Tests Included
Hematology	HCT, Hgb, MCH, MCHC, MCV, MPV, PLT, RBC, WBC, and differentials (neutrophils, lymphocytes, monocytes, eosinophils, and basophils relative and absolute)
Biochemistry	Albumin, alkaline phosphatase, ALT, AST, chloride, creatinine (enzymatic), GGT, glucose random, LDH, potassium, sodium, total bilirubin, triglycerides, urea (BUN), uric acid
Urine pregnancy test	For female subjects of childbearing potential (at each visit, except screening)
Laboratory tests required at screening only	β-hCG for female subjects of childbearing potential Serology (HBV (HBsAg, anti-HBc), HCV, HIV) TSH with reflex free T4 (ie, free T4 will be performed only if TSH value is abnormal)

Abbreviations: ALT, alanine aminotransferase; anti-HBc, antibody to hepatitis B core antigen; AST, aspartate aminotransferase; β-hCG, β-human chorionic gonadotropin; BUN, blood urea nitrogen; GGT, gamma-glutamyl-transferase; HBsAg, hepatitis B surface antigens; HBV, hepatitis B virus; HCT, hematocrit; HCV, hepatitis C virus; Hgb, hemoglobin; HIV, human immunodeficiency virus; LDH, lactate dehydrogenase; MCH, mean corpuscular hemoglobin; MCHC, mean corpuscular hemoglobin concentration; MCV, mean corpuscular volume; MPV, mean platelet volume; PLT, platelets; RBC, red blood cell (count); TSH, thyroid-stimulating hormone; WBC, white blood cell (count).

In case of a screening laboratory value abnormality, the test can be repeated once within the original screening time window, if the investigator believes there is a reasonable possibility that the subject would be eligible if re-tested.

If deemed appropriate by the investigator, clinically significant findings in clinical laboratory testing will exclude a subject from trial participation. Any clinically significant value will be reported as an AE.

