### **8.5.9 Adverse events of special interest (AESI)**

An AESI is an event type of scientific and medical concern specific for the product or development program, for which additional monitoring may be appropriate. Such an event might warrant further investigation in order to further characterize it.

Deep vein thrombosis/Pulmonary embolism is considered AESI in this trial and will require additional details to be recorded. LEO Pharma may request that the investigator forward additional test results, as appropriate. An AESI may be serious or non-serious. Serious AESIs require expedited reported via the SAE form as described in Section [8.5.7](#) in addition to the requirements specified below.

The additional information that will be collected is:

- Risk factors such as:
  - Previous thromboembolism (record as medical history)
  - Family history of deep vein thrombosis/pulmonary embolism or other cardiovascular/blood-clotting disorders
  - Genetic disorders that might increase the risk for thrombosis (record as medical history)
  - History of cancer (record as medical history)
  - Recent venous catheter placement (record as medical history)
  - Current smoker (record as tobacco smoking history)
  - Hormonal contraception/hormonal replacement therapy (record as concomitant medication)
  - Trauma or surgery (record as per protocol)
  - Immobilisation (e.g. prolonged bed rest or sitting for long periods)
  - None
- Method of verification may include:
  - Clinical evaluation
  - Image-verified
  - Laboratory test(s)

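### Lymphocytopenia is a named potential risk, but the protocol's laboratory tables count no subject with a low lymphocyte count; only an investigator-reported adverse event would

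*Combined protocol and SAP*

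**What the plan says.** Section 2.2.1 (Known Potential Risks) says lymphocytopenia was seen in oral nonclinical toxicity studies and could follow from systemic levels of delgocitinib. It concludes: "Lymphocytopenia is therefore considered an important potential risk for delgocitinib cream".

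The measurements exist. The hematology panel in Table 7 includes "differentials (neutrophils, lymphocytes, monocytes, eosinophils, and basophils relative and absolute". The Table 1 row "Clinical laboratory tests (biochemistry and hematology" is marked at Screening, Day 1, Weeks 4, 8, 12, 16, 20 and 24, and at early termination.

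The analysis is in Section 9.3.4.1: "Results from laboratory analyses and vital signs will be tabulated by treatment and visit using descriptive statistics", followed by "The value at each visit as well as the change from baseline will be presented descriptively". Section 9.3.1 defines the summaries as number of subjects, mean, SD, median, minimum, maximum and quartiles. Section 9.3.4.2 carries the approach into the open-label extension (OLE), with its own rule for the baseline.

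There is also an adverse event (AE) route. Section 8.2.4 states: "Any clinically significant value will be reported as an AE". Section 9.3.4.1 says the same of clinically significant changes, then summarises AEs by number of subjects and lists them by subject. It assigns an AE with onset on or after Week 12 to the OLE.

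The AE of special interest in Section 8.5.9 is a different event: "Deep vein thrombosis/Pulmonary embolism is considered AESI in this trial and will require additional details to be recorded".

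Section 9.3.1 leaves the details of safety definitions and analysis strategy to a separate SAP, to be prepared before database lock.

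**The concern.** Lymphocytopenia is something that happens to a subject: the count was in range and is now below it. The natural summary is how many subjects per arm that happened to. A table of values by visit does not give that number. It shows the lowest value at each visit, but not how many subjects were low, whether they were already low at baseline, or whether the same subject is low at successive visits.

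The AE route does count subjects, but only after a judgement for which the protocol gives no criterion. Section 8.5.5 also asks that an abnormal result be reported under the diagnosis behind it where possible, so cases may be spread over several preferred terms.

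Safety in the vehicle-controlled period is the trial's secondary objective. Without a subject-level count, the report may be unable to say how many subjects in each arm developed a risk that the sponsor itself names.

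**Working it through.** The plan states no figure on this point, so the check is a reading of the text, followed by an illustration.

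**1. What each planned output can answer**
- *How many subjects were ever low?* By-visit tables: no. AE tables: only those judged clinically significant.
- *Were they low at baseline?* By-visit tables: no. AE tables: in part, because the definition of a treatment-emergent event (Section 8.5.2) deals with conditions already present.
- *Is it the same subject at successive visits?* By-visit tables: no. AE listing: yes, for reported events.
- *Where do early-termination and unscheduled values go?* Not stated for the by-visit tables. Section 9.3.2 mentions unscheduled values only in defining baseline.

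**2. The Week 12 draw**
- Section 1.3 requires visit assessments before that visit's application of IMP unless otherwise specified, and no exception is given for blood samples.
- Table 1, footnote g, puts the first OLE application on the morning of Week 12.
- The Week 12 blood therefore reflects the randomised period.
- Under Section 9.3.4.1, a low value first found there and reported as an AE with that date becomes an OLE event.
- Week 12 is one of three scheduled post-baseline draws in the randomised comparison (Weeks 4, 8 and 12). For a vehicle subject, the event would be counted in the OLE although it arose before any delgocitinib.

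**3. Per-visit against ever-low counts**

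Inputs: about 15 subjects per arm (30 randomised 1:1, Section 6.3) and three draws. The probability of a low value at a visit is assumed to be 5%; the documents give none.
- Expected low at any one visit: 15 × 0.05 = 0.75.
- Ever low, if the same subjects are low at every visit: 15 × 0.05 = 0.75.
- Ever low, if visits are independent: 15 × (1 − 0.95³) = 15 × 0.1426 = 2.14.

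The number ever low is thus 0.75 to 2.1 of 15. At the lower end the visit table has the same expected count; at the upper end it is nearly three times as large. The planned tables cannot tell these cases apart.

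**4. Effect of individual falls on the arm mean**

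Assume a fall of 0.5 to 1.4 ×10⁹/L in one subject of 15. The mean change moves by 0.5/15 = 0.03 to 1.4/15 = 0.09 ×10⁹/L. The mean is a weak detector of one case. The minimum in the same table is not.

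**5. What a count could and could not show**

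If 0 of 15 are low, the one-sided 95% upper bound on the rate is 1 − 0.05^(1/15) = 18.1%. For 0 of 30 (everyone exposed to delgocitinib by the end of the OLE, if all enter it) it is 1 − 0.05^(1/30) = 9.5%. A count would describe the trial's subjects; it would not exclude a moderate rate.

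**The case against.** The strongest reply has three parts.

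First, a reader might infer that the plan never counts subjects with a low lymphocyte count. The documents do not support that. Clinically significant values become AEs, counted by subject and listed with onset relative to dosing. What stands is narrower: low values not judged clinically significant are not counted, and the judgement has no stated criterion.

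Second, a reader might infer that marked falls would vanish from the report. They would not, because the planned summaries include the minimum and quartiles of both value and change, so a large fall at a scheduled visit would be visible. What stands is that the table cannot turn a visible minimum into a number of subjects.

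Third, Section 9.3.1 defers safety detail to a separate SAP. Shift tables are the sort of detail such a document holds, and it may already contain them. This limits the claim to the protocol text.

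Two further readings should be resisted:
- Lymphocytopenia is not the only systemic harm named, since Section 8.5.9 names deep vein thrombosis/pulmonary embolism. Section 2.2.1 also reports low systemic exposure and generally no clinically significant laboratory changes with the cream.
- Section 6.2.1 says "The tubes will be weighed prior to dispensing and upon return", which might suggest that low counts should be related to the amount applied. The protocol promises no such analysis, and with a handful of low values it would tell little. Its absence is not a defect.

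**Conclusion.** The point holds for the protocol text. Lymphocytopenia is a named important potential risk and the counts are collected, but the stated laboratory analysis has no shift, lowest-value or below-range summary. Subjects are counted only through an AE that depends on unstandardised judgement, and a case first dated at Week 12 would be assigned to the wrong period.

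The size is modest. The illustration of 0.75 to 2.1 ever-low subjects of 15, against 0.75 per visit, rests on an assumed 5% per-visit probability and spans full persistence to independence between visits. The assumed falls behind the shift in means are likewise not from the documents. No safety inference is planned (Section 9.3.4.1), so no test or error rate is affected. What is lost is a plain descriptive count by arm. This is a cheap improvement worth making; it does not undermine the trial. If the separate SAP already provides the count, only confirmation is needed.

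**What to change.** In Sections 9.3.4.1 and 9.3.4.2, or by confirmation in the separate SAP before database lock, add for absolute lymphocytes, by arm and period:

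- (a) a shift table of baseline category against lowest on-treatment category, using the laboratory's own reference range;
- (b) the number and percentage of subjects ever below the lower limit of that range.

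State that pre-dose Week 12 values belong to the vehicle-controlled period, and that unscheduled and early-termination values are included in the period in which they fall. For the OLE, use the baselines in Section 9.3.4.2: the vehicle-controlled baseline for subjects first given delgocitinib, and the OLE baseline for subjects first given vehicle. Keep the by-visit summaries.

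The cost is two tables from data already in the database, with no new sample or visit. The reference range serves here only to classify values for display; it sets no rule for treating or withdrawing subjects. The downside is that some low values of no clinical importance will be shown.
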